# 8.5. Pharmacokinetics

For patients who progress to intubation in ICU, venous blood samples will be drawn on the days and times indicated in the SoA (Section 1.3).

These blood samples will be used to determine the plasma concentrations of baricitinib. Concentrations of baricitinib in human plasma will be determined by a validated liquid chromatography tandem mass spectrometry (LC/MS/MS) method.

The actual date and exact timing (24-hour clock) of sample collection and the date and time of study drug dosing should be recorded.

The sampling schedule should be followed as closely as possible; however, failure to take PK samples at the specified times will not be considered a protocol violation.

Only samples from patients receiving baricitinib will be assayed; samples from patients receiving placebo will not be assayed. PK samples will be kept in storage at a laboratory facility designated by the sponsor. PK results will not be provided to investigative sites.

Instructions for the collection and handling of blood samples will be provided by the sponsor. Samples will be analyzed at a laboratory approved by the sponsor.

#### Sample retention

The purpose of retention, the maximum duration of retention, and facility for long-term storage of samples is described in Appendix 10.1, Section 10.1.12.

## 8.6. Pharmacodynamics

This section is not applicable.

## 8.7. Genetics

This section is not applicable.

## 8.8. Biomarkers

Nasopharyngeal swab (to assess viral load and other characterizations), serum, and whole blood for RNA, epigenetic analysis and cellular phenotyping for exploratory nonpharmacogenetic biomarker research will be collected on days specified in the SoA (Section 1.3), where local regulations allow.

The baseline exploratory sample is essential to determining progressive viral load changes in the exploratory analysis during participation in the study. If, due to central lab kit supply, the first (Study Day 1) samples are not collected, it is not necessary to collect future exploratory biomarker central samples (NP swabs or blood samples); this will not be considered a protocol deviation. If the central lab kits are available, NP swabs and whole blood samples should be collected on study visit days per the SOA unless a phone visit is conducted and therefore the samples cannot be obtained; this would not be considered a protocol deviation.

## Sample use

Exploratory biomarker research is performed to address questions of relevance to drug disposition, target engagement, PD, mechanism of action, variability of participant response (including safety), and/or clinical outcome. Sample collection is incorporated into clinical studies to enable examination of these questions through measurement of viral load, biomolecules, RNA, proteins, lipids, and other cellular elements.

Samples may be used for research on the drug target, disease process, variable response to baricitinib, pathways associated with the studied disease, mechanism of action of baricitinib, and/or research methods or in validating diagnostic tools or assays related to the disease or to baricitinib.

## Confidentiality

All samples will be coded with the participant number. These samples and any data generated can be linked back to the participant only by the investigative site personnel.

## Sample retention

The purpose of retention, the maximum duration of retention, and facility for long-term storage of samples is described in Appendix 10.1, Section 10.1.12.

# 8.9. Immunogenicity Assessments

Immunogenicity is not assessed in this study.

# 8.10. Medical Resource Utilization and Health Economics

This section is not applicable.

## 9. Statistical Considerations

## 9.1. Statistical Hypotheses

#### Primary Objective

The primary objective of this study is to test the hypothesis that baricitinib 4-mg QD + background therapy is superior to placebo + background therapy in the treatment of hospitalized patients with COVID-19 infection, as assessed by the proportion of patients who die or require non-invasive ventilation/high-flow oxygen or invasive mechanical ventilation (including ECMO) by Day 28.

The primary objective will be assessed in the following populations

- Population 1- all randomized patients, and
- Population 2 -patients who, at baseline, require oxygen supplementation and are not receiving dexamethasone or systemic corticosteroids for the primary study condition

#### Testing Scheme for the Primary Analyses

The 1-sided p-values and associated test statistics are defined as

- p1 is the 1-sided p-value for Population 1; z1 is the associated test statistic
- p2 is the 1-sided p-value for Population 2; z2 is the associated test statistic

The hypotheses are

- H01 is the null hypothesis corresponding to Population 1
- H02 is the null hypothesis corresponding to Population 2

H01 will be rejected if:

•  $p_1 < \alpha_1 \text{ OR } (p_1 < 0.025 \text{ AND } p_2 < \alpha_2)$ 

H02 will be rejected if:

•  $p_2 < \alpha_2 \text{ OR } (p_2 < 0.025 \text{ AND } p_1 < \alpha_1)$ 

 $\alpha_1$  and  $\alpha_2$  are critical thresholds preserving the overall 1-sided type 1 study error at 0.025.

If either of the two tests is significant, then the study will be declared successful.

The testing scheme will provide a strong control of Type-I error for the study at a 1-sided 0.025 level and is based on the closed testing principle (Marcus et al. 1976). The testing scheme is parametric, where the known correlation is accounted for between the 2 test statistics  $z_1$  and  $z_2$ .

The  $\alpha_1$  for Population 1 will be pre-specified in the Statistical Analysis Plan (SAP). The  $\alpha_2$  for Population 2 will be calculated to control the study Type I error rate at 0.025, accounting for the prespecified value of  $\alpha_1$  and the correlation between the two test statistics. If the Population 1 test is rejected and the Population 2 test is not, or vice versa, the remaining  $\alpha$  will be recycled and used for subsequent testing of the population that was not significant (Millen and Dmitrienko 2011). The final  $\alpha$  levels will be based on the percentage of Population 2 within Population 1 observed in the final analysis data set. Additional details will be described in the SAP.

## 9.2. Sample Size Determination

In the protocol amendment C, it was assumed that the proportion of patients progressing to death or non-invasive ventilation/high-flow oxygen or invasive mechanical ventilation (including ECMO) by Day 28 was 28% and 18.5% for placebo and baricitinib, respectively. Accordingly, the sample size was increased to 600 to yield approximately 80% power to detect an absolute difference of 9.5% between the baricitinib treatment group and the placebo treatment group using a two-sided alpha of 0.05 with the provision that sample size may be updated in a blinded manner during the study from 600 up to approximately 1000, if warranted based on newly available external study data. This would include the various differing factors amongst the studies, including, for example, the ACTT-2 results.

In protocol amendment D, the sample size is updated based on newly available data from the ACTT-2 study (ACTT-2 press release 2020). Based on the emerging data and evolving therapeutic options for standard of care, the assumption for the proportion of patients in the placebo group progressing to death or non-invasive ventilation/high-flow oxygen or invasive mechanical ventilation (including ECMO) by Day 28 is revised to approximately 25%. The sample size of 1000 patients will yield approximately 47% power to detect an absolute difference of 5% and 83% power to detect an absolute difference of 7.5% between the baricitinib treatment group and the placebo treatment group using a two-sided alpha of 0.05.

In protocol amendment E, the sample size is updated to approximately 1400 patients based on blinded review of the proportion of patients requiring oxygen supplementation without the use of dexamethasone or systemic corticosteroids at baseline and the potential that concomitant use of systemic corticosteroids may reduce the magnitude of the treatment effect.

The table below describes the power calculations for various scenarios with a total sample size of 1400. This assumes, for illustration, that  $\alpha_1$  for Population 1 is 75% of the total alpha and that 60% of the patients were taking dexamethasone or other corticosteroids at baseline.

-	atients who are at OS 5 or baseline	Combined Effect Size	Power for at least one of the two primaries to succeed
Patients using dexamethasone or a systemic corticosteroid	Patients not using dexamethasone or a systemic corticosteroid		
0.075	0.075	0.075	81%
0.040	0.075	0.054	54%

Abbreviations: NIAID = National Institute of allergy and Infectious Diseases; OS 5 = #5 on the 8-point NIAID ordinal scale - Hospitalized, requiring supplemental oxygen; OS 6 = #6 on the 8-point NIAID ordinal scale - Hospitalized, on noninvasive ventilation or high-flow oxygen devices.

Note: Power estimates were obtained from a custom simulation program.

There is still significant uncertainty with these assumptions given the limited available data. Therefore, the sample size may be increased using an unblinded sample size re-estimation during an interim analysis (Gao et al. 2008).

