## COVID-19 pulmonary infection-related inclusion criteria

- [3] Hospitalized with coronavirus (SARS-CoV-2) infection, confirmed by polymerase chain reaction (PCR) test or other commercial or public health assay in any specimen, as documented by either of the following:
  - PCR positive in sample collected <72 hours prior to randomization; OR
  - PCR positive in sample collected ≥72 hours prior to randomization (but no more than 14 days prior to randomization), documented inability to obtain a repeat sample (for example, due to lack of testing supplies, limited testing capacity, results taking >24 hours, etc.) AND progressive disease suggestive of ongoing SARS-CoV-2 infection
- [4] Require supplemental oxygen at the time of study entry and at randomization.
- [5] Have indicators of risk of progression: at least 1 inflammatory markers >ULN (CRP, D-dimer, LDH, ferritin) with at least 1 instance of elevation >ULN within 2 days before study entry.

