Subgroup analyses for the primary and selected key secondary outcomes will evaluate the treatment effect across the following subgroups: baseline OS (OS 4 vs. OS 5 and OS 6 combined), baseline usage of remdesivir (Y/N), baseline usage of corticosteroids (Y/N), geographic region, duration of symptoms prior to enrollment, age, sex, dexamethasone and/or other systemic corticosteroid used at baseline for primary study condition, and comorbidities (if

applicable). Interaction tests will be conducted to determine whether the effect of treatment varies by subgroup.

Fisher's exact test will be used for TEAEs, discontinuations, and other categorical safety data for between-treatment group comparisons. Continuous vital signs, body weight, and other continuous safety variables, including laboratory variables, will be analyzed by an analysis of covariance (ANCOVA) with treatment and baseline value in the model. Shift tables for categorical safety analyses (for example, 'high' or 'low' laboratory results) will also be produced.

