	clarifying text about patients who	patients will remain on blinded 2-mg
	have eGFR $\geq$ 30 mL/min/1.73 m  to	dose (baricitinib or placebo) during
	<60 mL/min/1.73 m  at screening.	treatment.
5.1, Inclusion Criteria	Revised protocol inclusion criterion	Changed study population based on
	#4, stating that patients must require	ACTT-2 data availability and
	oxygen supplementation at entry and	population that derived greatest
	randomization.	benefit in recovery and mortality.
6.1, Study Interventions	Added bold font format and	To clarify for investigators; these
Administered	clarifying text about patients who	patients will remain on blinded 2-mg
	have eGFR $\geq$ 30 mL/min/1.73 m  to	dose (baricitinib or placebo) during
	$<60 \text{ mL/min}/1.73 \text{ m}^2$ at screening.	treatment.
		To clarify for investigators: Patients
	Added clarifying text about	who are discharged from hospital
	investigational product after patient's	will not be given investigational
	discharge from hospital.	product for home use.
6.5.3, Prohibited Concomitant	Added a clarification in a	Baricitinib for treatment of
Therapy	parenthetical phrase about prohibited	COVID-19 is required for certain
	concomitant medication.	participants according to the study
		design. However, JAK inhibitors are
		prohibited as concomitant therapy
		during the study.
6.6, Dose Modification	Added words "equal to or"; corrected	To provide consistency between text
	some symbols, replacing $>$ with $\ge$ .	statement and the "greater than or
		equal to" symbol $(\geq)$ in the
		preceding sentences.
7.1.1, Criteria for Permanent	Added a phrase about the Day 60	Regulatory feedback, as stated for
Discontinuation of Study	assessment.	Section 1.1
Drug		
8.1.1, COVID-19 Clinical Status	Added a statement about a Day 60	Regulatory feedback, as stated for
Assessment	assessment.	Section 1.1
8.3.1, Time Period and	Added a statement that serious	To clarify the SAE reporting process
Frequency for Collecting	adverse events, including death,	and to align with language already in
AEs and SAEs	caused by COVID-19 disease	Section 10.3.
	progression should not be reported	
	on the SAE form unless the	
	investigator deems them to be	
	possibly related to study treatment.	
9.2, Sample Size Determination	Moved the assumptions of the sample	To update the assumptions used to
	size as stated in amendment C, and	calculate the new sample size. The

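### Does the Amendment E power table need its unstated inputs (placebo rate, OS 4 share and effect) written in?

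*Protocol*

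**What the plan says.** Protocol 9.2 and SAP 5.2 carry the same table. It is introduced by "The table below describes the power calculations for various scenarios with a total sample size of 1400". For illustration, the text gives Population 1 75% of the alpha and assumes that "60% of the patients were taking dexamethasone or other corticosteroids at baseline". Two rows follow:

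- effect 0.075 on steroids and 0.075 off, combined 0.075, power 81%;
- effect 0.040 on steroids and 0.075 off, combined 0.054, power 54%.

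The power is the chance that at least one of the two primary tests succeeds. The SAP column header limits the effects to patients at OS 5 or OS 6. The only source given is the note "Power estimates were obtained from a custom simulation program".

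Protocol 9.1 defines the first test population as "Population 1- all randomized patients, and" the second as the oxygen-requiring patients not on steroids. OS 4 is a randomization stratum (Protocol 6.3, SAP 5.3) and a subgroup in Protocol 9.4.1 ("baseline OS (OS 4 vs. OS 5 and OS 6 combined"). Under the current inclusion criteria, patients must "Require supplemental oxygen at the time of study entry and at randomization". The amendment history dates that requirement to Amendment D.

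The last placebo rate in Protocol 9.2 belongs to Amendment D, where it "is revised to approximately 25" percent. The Amendment E paragraph neither repeats nor replaces it.

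**The concern.** This is the only power stated for the 1400-patient design, and a reader who tries the obvious calculation does not get it. The Amendment C and D figures follow from their printed inputs. The Amendment E figures do not follow if 25% placebo is carried forward and everyone is taken to be at OS 5 or OS 6: both rows come out more than ten points too high.

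The label on the combined effect adds to the doubt. It is an average over steroid use under an OS 5/6 heading. It equals the Population 1 effect only if OS 4 patients are absent or share the same average effect. Patients entered before the oxygen requirement could be at OS 4. A reader therefore cannot tell whether 1400 was sized on a Population 1 effect of 7.5 / 5.4 points or on something smaller. If the printed power were wrong, the stated basis for 1400 would be wrong too.

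**Working it through.** **Method.** Unadjusted two-proportion z with unpooled variance, SE = sqrt[(p0(1-p0) + p1(1-p1))/n per arm]. The planned test is covariate-adjusted logistic regression, so small differences are expected. Power for at least one success = 1 - Φ2(z_α1 - m1, z_α2 - m2; ρ), where m = effect/SE and ρ = sqrt(Population 2 share), the correlation given in SAP 6.6. Overall one-sided alpha is 0.025, with weights 0.75/0.25. Three readings of the split were tried:

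- Bonferroni: 0.01875 / 0.00625;
- weights kept and scaled up for the correlation;
- α1 fixed at 0.01875 and α2 solved for.

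**Earlier figures first.**

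- Amendment C, 300 per arm, 28% v 18.5%: 79.2% (stated about 80%).
- Amendment D, 500 per arm, 25% placebo: 47.5% for 5 points and 82.9% for 7.5 points (stated 47% and 83%).

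The method therefore matches the sponsor's earlier arithmetic.

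**Combined effect.** 0.6 × 0.040 + 0.4 × 0.075 = 0.024 + 0.030 = 0.054. This is correct, and it has no OS 4 term.

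**Reading A: 25% placebo, no OS 4.** There are 700 per arm in Population 1 and 280 per arm in Population 2; ρ = sqrt(0.4) = 0.632.

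- Row 1: SE1 = sqrt(0.331875/700) = 0.02177, so m1 = 0.075/0.02177 = 3.44. SE2 = sqrt(0.331875/280) = 0.03443, so m2 = 2.18.
- Row 2: SE1 = sqrt(0.345084/700) = 0.02220, so m1 = 0.054/0.02220 = 2.43; m2 is unchanged.

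**Reading B: 15% at OS 4 (assumption), event rate 10% and no effect there (assumptions).** OS 5/6 placebo is taken as 25.6% on and 30.6% off steroids. Shares are 0.15 OS 4, 0.51 on and 0.34 off.

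- Overall placebo = 0.15 × 0.10 + 0.51 × 0.256 + 0.34 × 0.306 = 0.250.
- Population 1 effect, row 1: 0.85 × 0.075 = 0.064. Row 2: 0.51 × 0.040 + 0.34 × 0.075 = 0.046.
- m1 = 2.90 / 2.05 and m2 = 1.85 (238 per arm); ρ = sqrt(0.34) = 0.583.

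**Reading C: no OS 4, 40% placebo (assumption).** m1 = 2.93 / 2.09, m2 = 1.85, ρ = 0.632.

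| Reading (N=1400) | Bonferroni | Scaled weights | α1 fixed |
|---|---|---|---|
| A | 91.7 / 68.2 | 92.3 / 69.6 | 91.8 / 69.6 |
| B | 80.3 / 54.4 | 81.2 / 55.7 | 80.5 / 55.7 |
| C | 80.8 / 54.8 | 81.8 / 56.4 | 81.0 / 56.3 |
| Printed | 81 / 54 | | |

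A binomial simulation of reading A (200,000 trials, pooled test, α1 fixed) gave 91.8% / 69.8%. One of reading B (400,000 trials) gave 80.2% / 53.8% with Bonferroni levels and 81.2% / 55.4% with scaled weights. With α1 fixed and no OS 4 patients, a pooled test needs a placebo rate of about 40% to give 81% and about 46% to give 54%.

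A grid over placebo rate, OS 4 share, OS 4 event rate and OS 4 effect found hundreds of combinations within two points of both printed figures, with OS 4 shares from 0 to 30% and OS 5/6 placebo rates from about 20% to 48%. The printed inputs do not fix the answer, but the printed answer sits inside the plausible range.

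**The case for a change.** The strongest case for acting is that Population 1 takes 99% of the final alpha (SAP 6.11.1), yet its planning effect is nowhere on record. A reader who takes the combined column as the all-randomized effect would overstate it by 7.5 - 6.4 = 1.1 and 5.4 - 4.6 = 0.8 points under reading B. The sponsor holds the simulation inputs, so a table note costs almost nothing.

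There is also an awkward match. With 25% placebo, no OS 4 patients and N=1000, the Amendment D size, power is 80.3-81.4% / 53.6-55.1%, which fits the table as well as reading B does.

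What stands is that the inputs are incompletely stated and that one natural reading misses by 11 points in the first row and 14 to 16 in the second. What does not stand is any inference of error. The N=1000 match is one fit among many. Both documents state 1400, and OS 4 dilution explains the figures at 1400 equally well. The OS 4 share, event rate and effect used here are back-fitted assumptions, so 6.4 / 4.6 points is no better documented than 7.5 / 5.4. The simulation may also have allowed for dropout, covariate adjustment or missing data, none of which is described for this table.

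**Conclusion.** No change follows. The gap is one of reporting. The placebo rate is not restated for Amendment E, and the OS 4 share, event rate and effect are not given. The printed 81% / 54% is not shown to be wrong. It is recovered to within about two and a half points by moderate OS 4 dilution at 25% overall placebo, or by a placebo rate near 40% with no OS 4 patients.

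The table no longer governs a decision. Both documents mark its alpha and steroid shares as illustrative. The 75% share gave way to 90% for the re-estimation (SAP 6.16.2) and 99% for the final tests (SAP 6.6 and 6.11.1). Protocol 9.2 concedes considerable uncertainty in the assumptions and provides for unblinded re-estimation, which the SAP bounds at about 1400 to 1700. The conditional power formula in SAP 6.16.2.2 uses the observed interim statistic, the stage sizes and alpha; it needs no planning placebo rate or effect. SAP 5.2 records that the interim took place in January 2021.

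Adding the inputs would make the table easier to check, but no sample size, test, alpha level or conclusion would differ. This rests on taking the stated N of 1400 at face value, which nothing in the documents contradicts.

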# 9.3. **Populations for Analyses**

The following populations are defined for this study:

Population	Description	
Entered	All participants who sign the informed consent form	
Intent-to-Treat (ITT)	All participants randomly assigned to study intervention. Participants will be	
	analyzed according to the intervention to which they were assigned.	
Per Protocol Set (PPS)	The PPS of the ITT population analysis set will include those participants who do not have any identified important protocol violations considered to impact efficacy analyses. Qualifications for, and identification of, significant or important protocol violations will be determined while the study remains blinded, prior to database lock.	
Safety	All participants randomly assigned to study intervention and who receive at least 1 dose of study intervention and who did not discontinue from the study for the reason 'Lost to Follow-up' at the first postbaseline visit. Participants will be analyzed according to the intervention they actually received.	
Follow-up	All randomized participants who received at least 1 dose of investigational product and have entered the post-treatment follow-up period. Participants will be analyzed according to the intervention which they received in the treatment period.	

A sensitivity analysis excluding patients who die within 24 hours of randomization and have Do Not Resuscitate (DNR) or Do Not Intubate (DNI) in ITT/PP analyses populations will be conducted.

## 9.4. Statistical Analyses

The statistical analysis of this study will be the responsibility of the sponsor or its designee.

Any change to the data analysis methods described in the protocol will require an amendment only if it changes a principal feature of the protocol. Any other change to the data analysis methods described in the protocol, and the justification for making the change, will be described in the SAP and clinical study report. Additional exploratory analyses of the data will be conducted as deemed appropriate.

The SAP will be finalized prior to unblinding. It will include a more technical and detailed description of the statistical analyses described in this section. This section is a summary of the planned statistical analyses of the most important endpoints, including primary and key secondary endpoints.

#### 9.4.1. General Considerations

Efficacy analyses will be conducted on the Intent-to-Treat (ITT) Population. Selected efficacy analysis may also be conducted using the Per Protocol Set. Safety analyses will be conducted on the Safety Population.

All tests of treatment effects will be conducted at a 2-sided alpha level of 0.05, unless otherwise stated.

Treatment comparisons of dichotomous efficacy variables between baricitinib 4-mg QD + background therapy and placebo + background therapy will be made using a logistic regression analysis with baseline stratification factors and treatment group in the model. The percentages,

difference in percentages, and 95% confidence interval (CI) of the difference in percentages will be reported. When logistic regression sample size requirements are not met (<5 responders in any category for any factor), the p-value from Fisher's exact test is produced instead of the odds ratio and CI.

Treatment comparisons for ordinal efficacy variables between baricitinib 4-mg QD + background therapy and placebo + background therapy will be made using proportional odds model with baseline stratification factors and treatment group in the model.

Treatment comparisons of continuous efficacy and health outcome variables will be made using analysis of covariance (ANCOVA) with baseline randomization factors and treatment group in the model, if the method is appropriate. Type III tests for least squares (LS) means will be used for statistical comparisons between treatment groups. The LS mean difference, standard error, p-value, and 95% CI may also be reported. The method used to handle missing data is described briefly in Section 9.4.1.3 and will be described in more detail in the SAP.

Treatment comparisons of ventilation-free days will be made using Wilcoxon rank sum test and will be described in more detail in the SAP.

When evaluating continuous measures over time, a restricted maximum likelihood-based mixed model for repeated measures (MMRM) may also be used. The model will include treatment, baseline randomization factors, visit, and treatment-by-visit-interaction as fixed categorical effects, and baseline score and baseline score-by-visit-interaction score (for endpoints other than baseline disease severity) as fixed continuous effects for endpoints other than baseline disease severity. An unstructured (co)variance structure will be used to model the between- and within-patient errors. If this analysis fails to converge, other structures will be tested. The Kenward-Roger method will be used to estimate the degrees of freedom. Type III sums of squares for the LS means will be used for the statistical comparison; the 95% CI will also be reported. Contrasts will be set up within the model to test treatment groups at specific time points of interest. Further details on the use of MMRM will be described in the SAP.

Log-rank test will be used as the primary analysis method for evaluating treatment effect in time-to-event endpoints. Kaplan-Meier curves and median survival will be estimated for each treatment group. Hazard ratio with 95% CI will be calculated using a Cox proportional hazards model with treatment as covariate and adjusted for baseline values of stratification factors. Diagnostic tests for checking the validity of the proportional hazards assumption may be performed. If the assumption of proportional hazards is not justified, a statistical model capable of handling nonproportional hazard will be explored to assess treatment effect, such as a max-Combo test (Lee 1996), restricted mean survival time model (Royston and Parmar et al 2013), and win ratio analysis (Pocock et al. 2012). An additional analysis may be performed to treat death as a competing event. The competing risk survival model, such as Fine-Gray model (Fine and Gray 1999) and cause-specific hazard model, will be considered. Further details on these methods will be described in the SAP.

Subgroup analyses for the primary and selected key secondary outcomes will evaluate the treatment effect across the following subgroups: baseline OS (OS 4 vs. OS 5 and OS 6 combined), baseline usage of remdesivir (Y/N), baseline usage of corticosteroids (Y/N), geographic region, duration of symptoms prior to enrollment, age, sex, dexamethasone and/or other systemic corticosteroid used at baseline for primary study condition, and comorbidities (if

applicable). Interaction tests will be conducted to determine whether the effect of treatment varies by subgroup.

Fisher's exact test will be used for TEAEs, discontinuations, and other categorical safety data for between-treatment group comparisons. Continuous vital signs, body weight, and other continuous safety variables, including laboratory variables, will be analyzed by an analysis of covariance (ANCOVA) with treatment and baseline value in the model. Shift tables for categorical safety analyses (for example, 'high' or 'low' laboratory results) will also be produced.

